If treatment of Group 1 has been terminated early due to a low therapeutic response rate, recruitment of participants into Group 2 will start. On Day 0, participants in Group 2 will receive a single loading dose consisting of 2 injections, each of which will contain 180 mg of teverelix TFA. The first injection will be administered as an intramuscular (IM) injection and the other as a subcutaneous (SC) injection (Stage 1). After Stage 1, participants in Group 2 will receive a maintenance dose, which will consist of a single 180 mg SC injection administered every 42 days.

If the serum T value (measured by the local laboratory) at the Day 21 visit is >2 ng/mL, the participant will then be withdrawn from the study. Participants will have their serum T measured by the local laboratory 1 week prior to each maintenance dose during Stage 2 of the study. If, at any point the local laboratory serum T result is >2 ng/mL the participant will be withdrawn from the study. Local laboratory serum T values ≤2 ng/mL allow the participants to continue in the study.

Total T (central laboratory) samples will be frozen and batch shipped to SGS (formerly Synlab), Münich for analysis every 3 months. Ad hoc shipments may be triggered if data review milestones require.

Study Procedures

The first IMP administration will be performed on an inpatient basis. IMP administration at consecutive visits may be performed on an outpatient basis. Study visits will be held as described below.

Screening Examination

The screening examination consists of the following assessments and procedures which will be performed within the 6 days prior to baseline assessments conducted on Day 0: determination of provision of informed consent; eligibility; medical and surgical history, especially for prostate cancer; previous medication; demographics; physical examination; body weight and height; serology (human immunodeficiency virus [HIV] and hepatitis); fasted (≥8 hours) safety laboratory tests; glycated haemoglobin (HbA1c); total T (local laboratory), triplicate 12-lead ECGs; and vital signs. As fasting is considered a study procedure informed consent must be obtained prior to asking the subjects to fast. Therefore, it may be necessary to conduct the screening visit over more than one day.

Stage 1 Visits for Group 1 and Group 2

Participants will attend study visits on Days 0, 1, 2, 3, 4, 7, 10, 12, 14, 21 and 28. At Day 0 (baseline visit), the loading dose of teverelix TFA will be administered.

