SC=subcutaneous; T=testosterone; TFA=Trifluoroacetate For participants in Group 2, the following actions will be taken at the Day 28 visit based on the results of the locally analysed T level determined from the Day 21 visit:

[T] (ng/mL)	Action Taken	Dose Administered
≤2	Continue with Stage 2 of Group 2	No dose on Day 28. Maintenance dose of 180 mg SC teverelix TFA every 42 days
>2	Withdraw from study; safety follow-up visit on Day 28	None

SC=subcutaneous; T=testosterone; TFA=Trifluoroacetate

Day 35 Visit

On Day 35, local testing of T levels will be performed to guide decision making at the Day 42 visit. PK, total T, LH, FSH and PSA (total and high-sensitivity [hs]) samples will also be collected for central laboratory analysis.

Stage 2 Visits in Groups 1 and 2

Day 28 Visit

Stage 2 will start at the Day 28 visit. However, participants will receive their first maintenance dose at the Day 42 visit and participants will visit the clinic at Day 35 to provide a blood sample for local laboratory testing of T levels.

Blood samples for PK and PD analyses (T, LH, FSH, PSA), and fasted (≥8 hours) safety laboratory testing will be collected. Samples will also be collected for urine analysis. AE assessment, physical examination, triplicate 12-lead ECG and assessment of vital signs (including sitting blood pressure and heart rate) will be performed.

If, in the opinion of the investigator, no safety concerns exist, participants will be discharged from the centre.

Visits at Day 42, Day 84, Day 126, and Day 168

On Day 42 the first maintenance dose will be administered.

Before administration of the maintenance dose, blood samples for PK and PD analyses as well as fasted (≥8 hours) safety laboratory testing will be collected. Samples will also be collected for urine analysis. Pre-dose AE assessment (including ISR), physical examination, triplicate 12-lead ECG and assessment of vital signs (including sitting blood pressure and heart rate) will be performed.

Participants will attend the clinic 1 week before each maintenance dose is given (i.e. at Days 35, 77, 119 and 161) to provide a blood sample for local laboratory assessment of T levels. At the Day 35 visit (only) PK, total T, LH, FSH and PSA (total and hs) samples will also be collected for central laboratory analysis. Based on the results of the local analysis of T level from 7 days prior to the scheduled visit, participants will receive:

[T] (ng/mL)	Action Taken	Dose Administered

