4.3 Participant Withdrawal Criteria

Premature study termination for an individual participant should be taken into consideration under the following circumstances:

- An illness/AE occurs during the study that influences the use, or the assessment of, the investigational medication
- He/she requires a forbidden concomitant medication (see Section 5.8.1)
- Adequate cooperation is not guaranteed

Decisions concerning study termination for individual participants will be made in accordance with the Medical Lead of the study and the Sponsor.

Premature study termination for an individual participant is mandatory under the following circumstances:

- Lack of efficacy and progressive disease (e.g. T levels >2 ng/mL)
- Lost to follow-up (the participant did not show up for the examination and the study personnel were unable to contact the participant)
- Death of the participant

The study must be terminated for an individual participant if the participant withdraws his/her consent or it is, in the investigator's opinion, necessary from a medical point of view (e.g. allergic reactions to the study medication).

If possible, a complete final examination, as planned for the visit that takes place on Day 168, should be carried out and documented on the corresponding pages of the electronic case report form (eCRF) for all participants who stop taking part in the study. If possible, the participant will also be asked to return to the site for a safety follow-up visit 28 days after the last administration of teverelix TFA.

Although participants may withdraw from the study at any time without giving any reasons, efforts should be made to find out the cause and document it.

For follow-up of participants' withdrawal because of an AE please see Section 6.3.7.3.

ANT-1111-02, Teverelix TFA in Prostate Cancer

FINAL Version 5.0, 31 May 2022

Page 37 of 84

Participants who terminate the study prematurely will not be replaced.

For criteria concerning the termination of the whole study please refer to Section 7.3.2.

5 Study Treatments

The IMP to be tested in this study is teverelix TFA, which is administered on Day 0 as a loading dose, followed by a maintenance dose as per the schedule below.

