#### **3.4 Intention-to-Treat (ITT) Analysis Set**

All participants included in the safety population and for whom the primary endpoint is evaluable will be included in the ITT analysis set. Participants for whom the primary efficacy measure is evaluable are those who have a non-missing central lab serum T record at Day 28.

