### 6.8.2 Secondary Efficacy Analyses

1. Proportion of participants achieving castration level with serum T <0.2 ng/mL or 0.6394 nmol/L at Day 28 will be analysed as mentioned in the Section 5.1.2 for both ITT and PP Population.
2. Proportion of participants achieving castration level with serum T <0.5 ng/mL or 1.73 nmol/L at Day 42 will be analysed as mentioned in the Section 5.1.2 for both ITT and PP Population.
3. Proportion of participants achieving castration level with serum T <0.2 ng/mL or 0.6394 nmol/L at Day 42 will be analysed as mentioned in the Section 5.1.2 for both ITT and PP Population.

---

Document:

C:\ProgramData\activePDF\Temp\DocConverter\API\Input\\$651f4dc0b253\$FE3041C5883446E892B20AB6D3F0E1BD.docx

Author: [name]

Version and Date: Version 1.0, 21 Apr 2023

Page 59 of 66

4. Proportion of participants achieving castration level with serum T <0.5 ng/mL or 1.73 nmol/L across treatment period from Day 28 until Day 168 will be analysed as mentioned in the Section 5.1.2 for both ITT and PP population.

*Note: Castration level is defined as the observed percentage of participants who have T concentrations <0.5 ng/mL (1.73 nmol/L) at all scheduled visits.*

Descriptive statistics with proportion, its Clopper-Pearson confidence interval (CI) and absolute frequencies.

5. Proportion of participants achieving castration level with serum T <0.2 ng/mL or 0.6394 nmol/L across treatment period from Day 28 until Day 168 will be analysed as mentioned in Section 5.1.2 for both ITT and PP population.

6. Time to T levels falling below castration level (<0.5 ng/mL [1.73 nmol/L]) for the first time. First time castrate serum level (<0.5 ng/mL [1.73 nmol/L]) will be defined as the analysis event. Analysis will be done from Day 1 to the end of the study.

The following censoring rules will be used for this analysis:

- Patients who did not achieve castrate serum T levels with central lab during the study period will be censored at their last serum T level assessment.
- Patients who leave the trial without achieving castrate serum T levels will be censored at their last serum T level assessment.

7. Time to (first) overstep of T castration level after achieving castration will be analysed using the Kaplan-Meier method.

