First time overstep of T castration level will be defined as the analysis event. Analysis will be done from the day of achieving castration T level to the end of the study. Only patients who achieved castration serum T levels will be analysed for both ITT and PP Population. Day of achieving castration T level will be defined as Day 1 for this analysis.

The following censoring rules will be used for this analysis:

- Patients with stable T level will be censored at their last available measure.
- Patients who fail to maintain castration T level will be censored at the day of failure.
- Patients who leave the trial for reasons other than a non-castrate serum T level will be censored at their last serum T level assessment.

*Note: Overstep of T castration level is defined as the first instance of T levels being above castration level after a patient has achieved castration.*

8. Time for serum T levels to be > 0.5 ng/mL after final, Day 168 injection will be analysed using the Kaplan-Meier method.

First time noncastrate serum T levels will be defined as the analysis event. Analysis will be done from Day 168 to the end of the observation. Only patients with castrate serum T levels at Day 168 will be analysed for both ITT and PP Population.

The following censoring rules will be used for this analysis:

- Patients who achieve and maintain castrate serum T levels with central lab from Day 168 through the end of the study period will be censored at their last serum T level assessment.
- Patients who leave the trial for reasons other than a non-castrate serum T level will be censored at their last serum T level assessment.

---

Document:

C:\ProgramData\activePDF\Temp\DocConverter\API\Input\\$651f4dc0b253\$FE3041C5883446E892B20AB6D3F0E1BD.docx

Author: [name]

Version and Date: Version 1.0, 21 Apr 2023

Page 60 of 66

9. Proportion of participants achieving castration level for LH (LH <1.1 U/L) at Day 28  
Descriptive statistics with proportion, will be analysed as mentioned in Section 5.1.2 for both ITT and PP population.
10. Proportion of participants with effective LH castration level across treatment period from Day 28 until Day 168. Descriptive statistics with proportion, will be analysed as mentioned in Section 5.1.2 for both ITT and PP population.
11. Time to LH levels falling below castration level (LH <1.1 U/L) for the first time will be analysed using the Kaplan-Meier method.  

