First time LH levels falling below castration level (LH <1.1 U/L) will be defined as the analysis event. Analysis will be done from Day 1 to the end of the study.  
The following censoring rules will be used for this analysis:
  - Patients who did not achieve castration LH level during the study period will be censored at their last LH level assessment.
  - Patients who leave the trial without achieving castration LH level will be censored at their last LH level assessment.
12. Time to (first) overstep of LH castration level after achieving castration will be analysed using the Kaplan-Meier method. First time overstep of LH castration level will be defined as the analysis event. Analysis will be done from day of achieving castration LH level to the end of the study. Only patients who achieved castration LH level will be analysed for both ITT and PP Population. Day of achieving castration LH level will be defined as Day 1 for this analysis.  
The following censoring rules will be used for this analysis:
  - Patients with stable LH level will be censored at their last available measure.
  - Patients who leave the trial for reasons other than a non-castrate serum T level will be censored at their last LH assessment.
13. Changes from baseline in PD parameters over time will be analysed as mentioned in Section 5.1.2 for both ITT and PP Population.
14. Confirmed PSA Response Rate will be analysed as mentioned Section 5.1.2 for both ITT and PP Population  
*Note: Confirmed PSA Response rate is defined as patients who have a > 50% reduction at day 14 followed with confirmation at day 28*
15. PSA Response Rate at day 28 will be analysed as mentioned Section 5.1.2 for both ITT and PP Population
16. Number of participants with a PSA response of ≥50% reduction at the Day 168 visit will be analysed as mentioned in Section 5.1.2 both ITT and PP Population.
17. Number of participants with PSA response of ≥80% reduction at the Day 168 visit will be analysed as mentioned in Section 5.1.2 for both ITT and PP Population.
18. Percent change from baseline in serum PSA concentration at each visit will be analysed as mentioned Section 5.1.2 for both ITT and PP Population.

---

Document:

C:\ProgramData\activePDF\Temp\DocConverter\API\Input\\$651f4dc0b253\$FE3041C5883446E892B20AB6D3F0E1BD.docx

Author: [name]

Version and Date: Version 1.0, 21 Apr 2023

Page 61 of 66

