## 7. Changes to the Planned Analyses

### 7.1 Changes to the Analyses Described in the Study Protocol and Protocol Amendments

Changes were made to the analysis definitions related to "Mean time to" events, which are now labelled as "Time to" events and will not contain the mean. This was changed due to the decision to use Kaplan-Meier methods of analyses for these, where the mean is not a suitable output in the presence of censoring.

After discussion with the FDA, a new Supplementary FDA Recommended Efficacy Analyses was added to the SAP.

The following analyses were also added:

PSA:

- PSA level at each visit
- Confirmed PSA Response Rate - defined as > 50% reduction in PSA from baseline at Day 14 followed with confirmation at Day 28
- PSA response rate at Day 28

FSH:

- FSH Level at each visit
- Percent Change From Baseline In Serum Concentrations Of FSH

LH:

- LH Level at each visit
- Percent Change From Baseline In Serum Concentrations Of Luteinizing Hormone

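### In the ITT analysis of time to first testosterone castration, men withdrawn for high testosterone who were never castrate are censored like any other leaver, so the tail of the Kaplan-Meier curve can only be too high

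*SAP*

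**What the plan says.** SAP 6.8.2 item 6 follows men from Day 1 to the end of the study, and the event is the first testosterone value below 0.5 ng/mL. On leavers it says: "Patients who leave the trial without achieving castrate serum T levels will be censored at their last serum T level assessment". Item 11 has the same rule for LH: "Patients who leave the trial without achieving castration LH level will be censored at their last LH level assessment". Neither rule depends on the reason for leaving.

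Item 11 names the estimator: "Time to LH levels falling below castration level (LH <1.1 U/L) for the first time will be analysed using the Kaplan-Meier method". Item 6 names none, but SAP 7.1 explains why the means were dropped from the time-to-event endpoints: "This was changed due to the decision to use Kaplan-Meier methods of analyses for these".

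The protocol (synopsis and section 5.5) ties withdrawal to response: "If, at any point the local laboratory serum T result is >2 ng/mL the participant will be withdrawn from the study". The first such decision uses the Day 21 sample. For Group 2 the synopsis table gives this action: "Withdraw from study; safety follow-up visit on Day 28". Protocol 4.3 makes stopping for lack of efficacy mandatory.

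Elsewhere the SAP does separate the reasons. Items 7, 8 and 12 of 6.8.2, and the supplementary analysis in 6.8.3, limit the censoring of leavers to exits not caused by non-castrate testosterone.

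Under SAP 6.8, efficacy is analysed on the per-protocol set and repeated on ITT. ITT membership needs a Day 28 sample (SAP 3.4): "Participants for whom the primary efficacy measure is evaluable are those who have a non-missing central lab serum T record at Day 28".

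**The concern.** Kaplan-Meier assumes that a censored man had the same future chance of the event as the men still at risk. A man withdrawn for testosterone above 2 ng/mL who was never below 0.5 ng/mL does not fit that assumption. He left because he did not respond, and he receives no further study drug. The never-castrate men who remain have values of 2 ng/mL or less and are dosed again at Day 42. Censoring the withdrawn man passes his probability to them.

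At stake is the upper part of the curve and any proportion read from it. The error has one direction, in favour of the drug.

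The situation is not remote. Group 2 opens only after Group 1 has stopped for low response, defined as three or more treatment failures, and protocol version 5.0 refers to Group 2 men already enrolled under version 4.0. By the protocol's own rule, Group 1 should therefore contain failures. How many of them were never castrate is not known.

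**Working it through.** **Plan's own figure.** The documents give no figure for time to first castration. The nearest is the Group 2 sample size (Protocol 8.1.12): 50 evaluable men, 74.5% against 90%, two-sided 5%, 80% power. By the normal approximation, n = [(1.960·√(0.745·0.255) + 0.842·√(0.90·0.10))/0.155]² = 50.99, against a stated 50; power at 50 is 79.0%. With 16% dropout, 50/0.84 = 59.5, so 60. The figure reproduces closely. It concerns the primary endpoint and is not touched by this point.

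**Set-up.** Take N men in the ITT set:
- w were never castrate and are withdrawn for testosterone, censored at about Day 28;
- r were never castrate and remain;
- k of those r first become castrate later;
- the other N − w − r men were castrate earlier;
- there is no other censoring.

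**Formulas.**
- 1 − KM = 1 − [(w + r)/N]·(1 − k/r)
- Cumulative incidence, with withdrawal as a competing event = (N − w − r + k)/N
- Difference = [(w + r)·k/r − k]/N = w·k/(r·N)

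The difference is never negative. It is zero when k = 0 and reaches its maximum, w/N, when k = r.

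**Illustration.** The counts are assumptions; the documents give none. N = 50, 45 ever castrate by Day 28, w = 3, r = 2.

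| k | 1 − KM | Cumulative incidence | Difference |
|---|---|---|---|
| 0 | 1 − 0.10·1 = 90% | 45/50 = 90% | 0 |
| 1 | 1 − 0.10·0.5 = 95% | 46/50 = 92% | 3 points |
| 2 | 1 − 0.10·0 = 100% | 47/50 = 94% | 6 points |

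For scale, the binomial standard error is √(0.92·0.08/50) = 3.8 points at 92% and √(0.94·0.06/50) = 3.4 points at 94%.

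A smaller group is more sensitive. Group 1 is analysed separately; with N = 20, w = 2 and r = k = 1 (again assumed), the curve ends at 100% against 18/20 = 90%.

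**Median.** With most men castrate before the first efficacy withdrawal at Day 28, the median is reached earlier and is the same in every case.

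**Which set.** The per-protocol set requires completion of the study (SAP 3.7), so these men are excluded from it, not censored. A man who leaves without a Day 28 central testosterone is in neither set. The mechanism therefore acts only in the ITT repeat, on withdrawn men who have a Day 28 central value.

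**The case against.** **The size may be zero.** Protocol 1.2.2 reports castration within 3 days in most men with advanced prostate cancer, sometimes followed by breakthrough. A man who falls below 0.5 ng/mL early and later exceeds 2 ng/mL is already an event in item 6. Only men never below 0.5 ng/mL at any central sample can cause the bias, and only if another never-castrate man converts later. The documents do not say that a maintenance dose induces castration in men whom the loading dose left above the threshold. This stands, and it is why the size is given as a formula with a range.

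**Sizes taken from the sample-size rates.** A reader might infer from the 90% and 74.5% rates that 5 or 13 of 50 men are never castrate. With 13 such men, w = 6, r = 7 and k = 5, the shift would be 30/350 = 8.6 points. The documents do not support this. Those rates concern testosterone at Day 28, whereas item 6 counts the first castrate value at any time. The never-castrate count cannot exceed the Day 28 non-responder count and may be well below it.

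**The proportion is not a planned output.** The SAP does not commit to reporting 1 − KM as a proportion ever castrate; castration proportions come from other items as counts. This stands, but a Kaplan-Meier curve still shows its plateau.

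**The contrast with other items is partly natural.** In items 7 and 8 and in 6.8.3, non-castrate testosterone is itself the event. That explains their wording, but it does not make the exit uninformative in item 6.

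**LH is indirect.** Withdrawal is triggered by testosterone, and a man withdrawn for it may already have met the LH threshold. This stands, and no LH size is claimed.

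**Conclusion.** The point holds for the ITT analysis of item 6. As written, the rule censors non-response as if it carried no information, and the tail of the curve can then be too high but not too low. The overstatement is w·k/(r·N): nil if no remaining never-castrate man converts later, 3 or 6 points in the illustration, and never more than w/N. These sizes rest on assumed counts, on all later conversions following the withdrawals, and on no other censoring.

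Two stronger readings go too far. A reader might infer that the per-protocol result is biased by this censoring. It is not: that set leaves the men out, which raises a separate question about who is in the denominator. A reader might also infer that the withdrawn men had persistently high testosterone, but a single local value above 2 ng/mL is enough. The median, the primary endpoint and the sample size are unaffected. This is a modest correction to a descriptive secondary analysis.

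**What to change.** In SAP 6.8.2 item 6, for the ITT set:
- treat withdrawal for non-castrate testosterone before first castration as a competing event, and report the Aalen-Johansen cumulative incidence;
- keep censoring for exits unrelated to testosterone, and for men still under observation at the end;
- report beside the curve the crude number ever castrate over all men in the set.

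Use the same handling in item 11, with a note that the link to LH is indirect. The withdrawal reasons that SAP 4.3.2 already plans to summarise can identify these men.

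The cost is about two sentences in the SAP and one option in the SAS procedure, with no new data. The reported plateau may be slightly lower.

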8.1.4 Secondary Endpoint Analyses

Secondary Endpoints

- 1. Proportion of participants achieving castration level with serum T <0.2 ng/mL at Day 28
- 2. Proportion of participants achieving castration level with serum T < 0.5 ng/mL at Day 42
- 3. Proportion of participants achieving castration level with serum T <0.2 ng/mL at Day 42
- 4. Proportion of participants achieving a T castration rate over 168 days of treatment period

Note: Castration rate is defined as the observed percentage of participants who have T concentrations < 0.5 ng/mL (1.73 nmol/L) at all scheduled visits.

- 5. Proportion of participants achieving profound castration rate (<0.2 ng/mL) over 168 days of treatment period
- 6. Mean time to T levels falling below castration level (<0.5 ng/mL [1.73 nmol/L]) for the first time
- 7. Mean time to (first) overstep of T castration level after achieving castration
- 8. Mean time for serum T levels to be ≥ 0.5 ng/mL after final, Day 168 injection
- 9. Proportion of participants achieving castration level for LH (LH <1.1 U/L) at Day 28
- 10. Proportion of participants with effective LH castration rate over 168 days of treatment period
- 11. Mean time to LH levels falling below castration level (LH <1.1 U/L) for the first time
- 12. Mean time to (first) overstep of LH castration level after achieving castration
- 13. Changes from baseline in PD and PK parameters over time

- 14. Number of participants with a PSA response of ≥50% reduction at the Day 168 visit
- 15. Number of participants with PSA response of ≥80% reduction at the Day 168 visit
- 16. Percent change from baseline in serum PSA concentration at each visit
- 17. Mean serum PSA concentration at each visit
- 18. Mean serum LH concentration at each visit
- 19. Mean serum T concentration at each visit
- 20. Mean serum FSH concentration at each visit

The secondary efficacy parameters will be analysed in an exploratory manner using descriptive statistics.

Secondary efficacy variables will be summarised by number of available values, minimum, Quartiles 1 and 3e, median, mean, SD, maximum, and 95% CI for the mean if appropriate. Categorical data will be presented by frequency and percentage.

These parameters are according to the secondary endpoints:

- Percentage of participants who have T concentrations <0.2 ng/mL at the end of Stage 1 (Day 28)
- Percentage of participants who have T concentrations <0.5 ng/mL and < 0.2 ng/mL at all scheduled visits

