- Percentage of participants who have LH concentrations <1.1 U/L at all scheduled visits
- Time to T levels falling below castration level (<0.5 ng/mL) for the first time
- Time to first T concentration ≥0.5 ng/mL after castration has been achieved
- Time to LH levels falling below castration level (<1.1 U/L) for the first time
- Time to first LH concentration ≥1.1 U/L after castration has been achieved
- PD (LH, FSH, PSA, T) and PK (teverelix TFA concentrations) parameters over time (see Sections 6.4 and 6.5) and their changes from baseline
- Serum PSA concentration at each visit including absolute and relative change from baseline
- Number of participants with a PSA response of ≥50% reduction at the Day 168 visit compared to baseline
- Number of participants with a PSA response of ≥90% reduction at the Day 168 visit compared to baseline
- Serum LH concentration at each visit
- Serum FSH concentration at each visit

PK/PD parameters will be analysed by measuring actual times for each concentration. Descriptive statistics will be based on the scheduled times. The participants' concentration-time curves will be presented graphically per parameter.

Further details regarding PK/PD analyses, including scale transformations, parameter formulas and determination of terminal rate will be detailed in the SAP.

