#### **6.8.3      Supplementary FDA Recommended Efficacy Analyses**

Supplementary analysis will be conducted utilizing the Kaplan-Meier technique to estimate the proportion of patients who achieve and maintain castrate T levels (<0.5 ng/mL or 1.73 nmol/L) from Day 28 through the end of the treatment period using the ITT population.

Treatment failure [non-castrate serum T levels ( $\geq 0.5$  ng/mL or 1.73 nmol/L) with central lab] will be defined as the analysis event.

The following patients will be considered as experiencing an event

1. Patients who did not achieve castrate serum T levels (<0.5 ng/mL or 1.73 nmol/L) by Day 28. Day 28 will be considered as the day of event.
2. Patients who successfully achieve a castrate serum T level by Day 28 but fail to maintain it throughout the treatment period. Day of failure (day of sampling) will be considered as the day of event.

---

Document:

C:\ProgramData\activePDF\Temp\DocConverter\API\Input\\$651f4dc0b253\$FE3041C5883446E892B20AB6D3F0E1BD.docx

Author: [name]

Version and Date: Version 1.0, 21 Apr 2023

Page 62 of 66

The following patients will not be considered as having experienced an event:

[figure not shown]
- 1 Patients who achieve and maintain castrate serum T levels with central lab from Day 28 through the end of the treatment period.
- 2 Patients who leave the trial for reasons other than a non-castrate serum T levels.

Censoring and handling of missing data rules will be used for this analysis:

[figure not shown]
- 1 Patients who achieve and maintain castrate serum T levels with central lab from Day 28 through the end of the treatment period will be censored at their last serum T level assessment.
- 2 Patients who leave the trial for reasons other than a non-castrate serum T level will be censored at their last serum T level assessment.
- 3 Patients with one or more consecutive missing serum T levels and a non-castrate serum T level after the missing time point(s) will be considered to have had an event (treatment failure) at the first missing time point. For example: if the subject's data is missing for Days 28 and 35 and having a non - castrate T levels ( $\geq 0.5$  ng/mL) on Day 42 we should consider that the subjects had an event on day 28.

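### SAP 6.8.2 item 7 defines the first testosterone overstep as the Kaplan-Meier event and then censors that same overstep, so the rule as written leaves no events

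*SAP*

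**What the plan says.** SAP 6.8.2 item 7 sets the method: "Time to (first) overstep of T castration level after achieving castration will be analysed using the Kaplan-Meier method". The event is stated directly: "First time overstep of T castration level will be defined as the analysis event". A note defines overstep as the first T above the castration level once castration has been achieved. Only participants who achieved castration are analysed, and the day they did so is Day 1 of the time scale.

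Three censoring rules follow:

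1. Participants with stable T are censored at their last measurement.
2. "Patients who fail to maintain castration T level will be censored at the day of failure".
3. Participants who leave for a reason other than non-castrate T are censored at their last T assessment.

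On the time span, item 7 says: "Analysis will be done from the day of achieving castration T level to the end of the study".

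Protocol 8.1.4 describes the endpoint as "Time to first T concentration ≥0.5 ng/mL after castration has been achieved" and gives the status of all secondary endpoints: "The secondary efficacy parameters will be analysed in an exploratory manner using descriptive statistics".

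**The concern.** Rule 2 censors the occurrence that item 7 has just defined as its event. A Kaplan-Meier curve falls only at events. If every overstep is coded as censored, the estimate cannot fall and the median cannot be estimated. The output would look like perfect maintenance of castration however many participants lost it.

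The endpoint is not a full duplicate of other analyses. Item 4 and SAP 6.8.3 assess maintenance from Day 28. Central-laboratory T is also sampled repeatedly before then (Protocol Table 14), and Protocol 1.2.2 reports transient breakthrough in earlier participants. A loss that is re-suppressed by Day 28 would appear as a time-to-event outcome only in item 7.

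**Working it through.** The documents give no rate, median or event count for item 7, so there is no stated figure to reproduce. The check is first logical and then illustrated numerically.

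**Step 1: classify everyone analysed.** Each participant has achieved castration and then does one of three things.

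| What happens next | Rule that applies | Coding as written |
|---|---|---|
| T stays castrate | 1 | Censored |
| T rises out of the castrate range | 2 | Censored on the day of failure |
| Leaves for another reason before any rise | 3 | Censored |

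No category is left for an event. A T of exactly 0.5 ng/mL does not change this: it is a failure to maintain a level below 0.5, so oversteps remain a subset of failures.

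**Step 2: compare with the related text.**

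- Protocol 8.1.4 makes the first T ≥0.5 ng/mL after castration the endpoint itself.
- SAP 6.8.3, on participants who achieve but do not maintain castration: "Day of failure (day of sampling) will be considered as the day of event".
- SAP 6.8.2 item 12, the parallel LH analysis: "First time overstep of LH castration level will be defined as the analysis event". It censors stable participants and those leaving for other reasons, and has no rule censoring failures.
- SAP 6.8.2 item 8, T recovery after the Day 168 injection, has no such rule either.
- SAP 7.1 explains the move from mean times to Kaplan-Meier and records no decision to censor failures.

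**Step 3: size of the distortion.** Assumed inputs: n = 50 (the evaluable Group 2 number in Protocol 3.1 and 8.1.12), all castrate by study Day 3, no earlier censoring, and k losses spread over Days 42, 84, 126 and 168. The product-limit estimate is S = ∏(1 − d/r), with d events among r at risk. Without earlier censoring it telescopes to 1 − k/50. For k = 8, two per visit:

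48/50 × 46/48 × 44/46 × 42/44 = 42/50 = 0.84.

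| Losses k | S at Day 168, loss = event (Greenwood SE) | S at Day 168, rule as written |
|---|---|---|
| 3 | 0.94 (0.034) | 1.00, 0 events |
| 5 | 0.90 (0.042) | 1.00, 0 events |
| 8 | 0.84 (0.052) | 1.00, 0 events |
| 10 | 0.80 (0.057) | 1.00, 0 events |
| 15 | 0.70 (0.065) | 1.00, 0 events |

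**Step 4: the time span (secondary).** Dosing ends at Day 168, but Stage 3 follows Group 2 participants to Day 252 or until local T is ≥1 ng/mL. With losses coded as events and follow-up running to the end of the study, off-drug recovery also counts as overstep. Take k = 8 and assume that the other 42 all enter Stage 3. The documents give no recovery rate, so a range is shown.

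| Recover by Day 252 | S at Day 168 | S at Day 252 | Events |
|---|---|---|---|
| 0 | 0.84 | 42/50 = 0.84 | 8 |
| 11 | 0.84 | 31/50 = 0.62 | 19 |
| 21 | 0.84 | 21/50 = 0.42 | 29 |
| 32 | 0.84 | 10/50 = 0.20 | 40 |
| 42 | 0.84 | 0/50 = 0.00 | 50 |

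The on-treatment estimate does not move; the tail, the event count and possibly the median do. If follow-up ended at Day 168, the median would not be reached. With Stage 3 included, 18 recoveries bring S to 24/50 = 0.48 and the median is reached. At 17, S is exactly 0.50 and the answer depends on the software's convention.

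**The case against.** The strongest counter-argument is that zero events is only one reading. The event sentence is as literal as the bullet, and the SAP ranks neither above the other. Under the usual convention, an event and a censoring time on the same day count as an event, so the bullet might only mean that follow-up stops there. The SAP does not state that convention for item 7, however, and a list of censoring rules is normally programmed as a list of participants to censor.

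A second reading gives the bullet a narrower purpose. Participants are withdrawn on local T >2 ng/mL, and Days 77, 119 and 161 have local samples only (SAP Table 7). Someone withdrawn then may have no central overstep, and neither rule 1 nor rule 3 fits him. Rule 2 may have been meant for this case. Its wording does not say so, and censoring such participants would be informative because it removes clear failures. What stands is that the correction should say how they are handled.

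It is also fair that the intent can be recovered from other text, and that a careful programmer would probably query the bullet. A loss before Day 28 that persists to Day 28 is still caught by the primary endpoint and item 4. Running to the end of the study is a stated choice. On-treatment maintenance is reported in item 4 and 6.8.3, and off-drug T recovery in item 8, so the Stage 3 point is the weaker of the two. The illustration uses assumed counts. Not every Group 2 participant need enter Stage 3, since the Protocol Synopsis lets ongoing participants stay on version 4.0.

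**Conclusion.** The concern holds. Item 7 contradicts itself, and the protocol, SAP 6.8.3 and item 12 all show that loss of castration is the event. Applied as written, the censoring list yields 0 events and a curve fixed at 100%; the correct estimate in the illustration runs from 94% to 70% for 3 to 15 losses among 50. That size rests on the assumed counts and on no earlier censoring. The conclusion of no events rests only on letting the censoring list govern.

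The scope is limited to one exploratory secondary endpoint. The primary Day 28 proportion, item 4 and the 6.8.3 analysis are unaffected. It should be fixed, but it does not threaten the trial's main conclusion. The open-ended time span in items 7 and 12 is a secondary matter of clarity.

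**What to change.** **Main change.** Delete the second censoring bullet in item 7 and count these participants as events on the date of the sample showing the overstep, as 6.8.3 does. State that central-laboratory T determines the event, and say how a participant withdrawn on a local result with no central overstep is dated and coded.

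**Secondary change.** For items 7 and 12, state an analysis cut-off that separates on-treatment overstep from recovery after the last dose, or report the on-treatment and Stage 3 periods separately. Say how samples within 42 days of the Day 168 dose are treated: Day 203 (168 + 35) and Day 210 (168 + 42) in Stage 3, and the follow-up sample at about Day 196 (168 + 28) for participants without Stage 3.

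**Cost.** One deleted bullet and a few clarifying sentences, with no new data and no burden on participants. SAP 7.2 rules out changes to Version 1.0 after database lock, so this should be done before then.
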